Several studies have found that physical activity may be an effective intervention to enhance QOL in cancer survivors.²⁴⁻²⁶ Physical activity has been reported to decrease fatigue, anxiety, and depression²⁷⁻³¹, and to improve sleep among healthy adults^{30,31}. More than one third of the decline in functional capacity experienced by cancer patients can be attributed to prolonged physical inactivity³². Prolonged physical inactivity and sedentary lifestyle can lead to rapid losses in fitness, energy, and physical functioning³³. Decreased physical activity may also worsen complaints of cancer related fatigue²⁵. Aerobic exercise training has been found to significantly lower levels of fatigue in patients undergoing RT; however, the mechanism underlying this positive effect is unclear^{7,11,34-36}. Despite the uncertainty about the precise contributions of diverse mechanistic pathways and the timing of introducing an exercise regimen, enough evidence exists of the potential utility of increased exercise to warrant further controlled intervention studies.

e. Methods, including statistical analysis

Study Design

This RCT targets women with breast cancer stages 0-IIIA scheduled to receive RT (no T4, N3, or M1 disease). After obtaining written informed consent, participants are randomized either to a structured moderate-intensity aerobic training exercise regimen concurrent with radiotherapy or to a control group. Endpoints are assessed at baseline, 4 weeks into the radiation course, and at the 4-week follow-up visit. In order to minimize loss to follow up, visits coincide with radiation appointments. Participants in the structured exercise group are instructed to use portable stationary pedal exercisers to achieve an exercise goal of 75 minutes/week of moderate-intensity exercise. All exercise sessions are supervised and conducted in the RT facility while patients are waiting for their RT or after their RT. Radiation therapy is typically administered on a five-times-weekly schedule, amounting to 15 minutes of exercise per weekday. Control group participants are asked to maintain their normal physical activity levels.

Eligibility Criteria

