Participants will be randomly assigned to structured moderate-intensity aerobic exercise program or to the control group using a block randomization scheme. The study biostatistician ([name].) will generate the computer-based randomization sequence. The intervention assignment is placed in opaque envelopes and delivered to the study coordinator. After completing baseline assessments, eligible participants will be assigned to study arm by a study coordinator who will open the next one of the sequentially-numbered, sealed envelopes.

Intervention

Arm 1: Exercise Intervention Arm

Participants randomized to the exercise intervention will be required to exercise before or after each radiation treatment session, on a five-treatment per week schedule. No special accomodations will be made to open the clinic on weather days or on extra days in the event of machine failure or patient unavailability. The exercise intervention will be administered at the radiation treatment facility in a room allocated for the study. The exercise prescription consists of aerobic training utilizing the portable stationary pedal exerciser (Pedlar) which contains two cycling pedals mounted to a stationary block that allows patients to exercise while sitting. Pedal tension is adjusted to provide desired resistance. Exercise intensity is self-rated by participants, instructed that moderate intensity goal will "make you breathe somewhat harder than normal". Participants may move and position the device to permit comfortable use while sitting in a chair. Participants are required to perform 15 minutes/day of aerobic exercise using the Pedlar device on radiation treatment days; during a standard radiation course, this will typically yield 75 minutes/week of aerobic time. Ten Pedlar devices have been approved for purchase for HUMC Department of Radiation Oncology through the Development Grant. Participants will record their activity on a daily basis on an exercise log (Appendix H).

Arm 2: Control Arm

Control group participants will be told to maintain their current daily activities and exercise habits for the duration of their treatment.

Study retention and adherence

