All participants in the study undergo RT as scheduled by their physician. The exercise intervention does not interfere with dose or timeline of RT. No specific requirements are made herein regarding prone or supine positioning, utilization of standard fractionation or hypofractionation, use of cardiac blocking or for utilization or omission of boost phase of radiation. These treatment decisions are completely at the discretion of the treating radiation oncologist. Adherence to the exercise intervention is achieved by offering participants flexibility in scheduling daily exercise, either before or after radiation treatment. Adherence is recorded in daily participation logs. Logs document participant identification, date, and length of time utilizing the Pedlar device. Participant retention efforts include a \$20 gift card incentive at baseline and one follow-up visit.

Assessments

Three assessments: at baseline, at 4-weeks into radiation course and at 4-week follow-up visit, will be assessed (see Table 1 below).

Table 1: Baseline and Follow-up Assessments

Assessment	Screening	Baseline (T0)	4 weeks (T1)	Follow-up visit (T2)
Eligibility (Appendix A)	X			
Informed Consent (Appendix B)	X			
Demographics (Appendix C)	X			
Medical history (Appendix C)	X			
Medications (from MD Consultation Note)	X			
Cancer and Treatment Summary (Appendix D)	X			
Performance Status	X			
Physical activity readiness questionnaire (Appendix C)	X			
Physical activity recall questionnaire (Appendix E)	X			
Blood tests for hematology (Appendix F)		X		
Vital signs and anthropometrics (Appendix G)		X	X	X
FACIT-Fatigue (in Appendix C)		X	X	X
FACT-B HRQOL (in Appendix C)		X	X	X
Inflammation biomarkers (Appendix F)		X	X	X
Adverse events assessments			X	X
Radiation Treatment Summary (by Treating MD)				X

Outcomes

Primary outcomes

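### Adverse events are asked about only at T1 and T2, so a woman who withdraws before week 4 has no scheduled adverse event record, and the log as described does not show why a session was shortened or missed.

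*Combined protocol and SAP*

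**What the plan says.** In section e, Methods, the Assessments paragraph sets the study contacts: "Three assessments: at baseline, at 4-weeks into radiation course and at 4-week follow-up visit, will be assessed". In Table 1 the row "Adverse events assessments" is ticked under T1 and T2 and nowhere else. The text available contains no other adverse event procedure: no definition, grading, question at sessions, or check at withdrawal. The Statistical analysis section names no adverse event summary or comparison.

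Under Intervention, women in Arm 1 must "exercise before or after each radiation treatment session, on a five-treatment per week schedule", and "during a standard radiation course, this will typically yield 75 minutes/week of aerobic time". Study Design adds a safeguard: "All exercise sessions are supervised and conducted in the RT facility while patients are waiting for their RT or after their RT".

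Under Study retention and adherence, the daily record is described in one sentence: "Logs document participant identification, date, and length of time utilizing the Pedlar device". The same section leaves course length open: "No specific requirements are made herein regarding prone or supine positioning, utilization of standard fractionation or hypofractionation". The Arm 1 text itself foresees sessions lost to weather, machine breakdown or absence of the patient.

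**The concern.** Exposure to the intervention is daily, but the safety question comes twice, the first time four weeks in. The women least likely to reach that question are those who leave early, and a symptom brought on by exercise is one plausible reason for leaving. Missing adverse event data would then depend on the events themselves.

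The log has the same weakness for Aim 2, which promises data on acceptability and adherence. A bare count of minutes treats a session cut short by a symptom and one cancelled by a machine fault as the same thing. For a trial meant to support a larger one (section g, Future Plans), the difference between women who could not tolerate the exercise and a clinic that was closed is information the next design needs. It cannot be recovered afterwards.

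**Working it through.** No power or sample size figure is in dispute. The check is schedule arithmetic and a comparison of sections.

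**Inputs from the document.** 15 minutes on each treatment day and five treatment days a week (Intervention, Arm 1); T1 at 4 weeks into radiotherapy (Assessments); adverse events at T1 and T2 only (Table 1).

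**The plan's own figure.** 15 × 5 = 75 minutes a week, which agrees with the text.

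**Exposure before the first question.** 5 × 4 = 20 sessions; 20 × 15 = 300 minutes. This is a maximum, assuming full attendance and a course of at least 20 fractions.

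**Course length.** The document gives none, so the number of fractions *f* below is assumed, at five a week. Sessions up to T1 = min(*f*, 20); sessions after T1 = max(0, *f* − 20); weeks from last session to T1 = max(0, 4 − *f*/5). If T2 is 4 weeks after radiotherapy ends (also an assumption), the time from T1 to T2 is (*f*/5 + 4) − 4 = *f*/5 weeks.

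| *f* | Weeks of RT | Sessions up to T1 | Sessions after T1 | Last session to T1 (weeks) | T1 to T2 (weeks) |
|---|---|---|---|---|---|
| 15 | 3.0 | 15 | 0 | 1.0 | 3.0 |
| 16 | 3.2 | 16 | 0 | 0.8 | 3.2 |
| 19 | 3.8 | 19 | 0 | 0.2 | 3.8 |
| 20 | 4.0 | 20 | 0 | 0 | 4.0 |
| 25 | 5.0 | 20 | 5 | 0 | 5.0 |
| 28 | 5.6 | 20 | 8 | 0 | 5.6 |
| 30 | 6.0 | 20 | 10 | 0 | 6.0 |
| 33 | 6.6 | 20 | 13 | 0 | 6.6 |

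**Long courses.** With 25 to 33 fractions, 5 to 13 sessions fall after T1, and their events are first asked about at T2. Recall is then about 4 to 6.6 weeks if T2 is counted from the end of radiotherapy. If T2 is 4 weeks after T1, recall is at most 4 weeks. The document does not say from which point the follow-up visit is counted.

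**Short courses.** With 15 to 20 fractions, all exercise is over by T1, but the woman is still due to be asked there, at most about a week late. A course shorter than 15 fractions would lengthen that delay by the same formula, but it would still be a delay and not a loss.

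**When T1 falls.** Three statements do not fit together for every course. Assessments puts T1 at week 4. Study Design says visits fall on radiotherapy appointments, which week 4 cannot do once a course shorter than 20 fractions has ended. Statistical analysis labels the 4-week score as the end of radiotherapy, which is untrue for a longer course. All three hold only when the course is 20 / 5 = 4 weeks. If T1 means the last treatment day, essentially all exercise precedes the first question whatever the course length.

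**Early withdrawal.** This needs no assumption about course length. A woman who leaves before T1 and does not attend it meets no ticked cell in the adverse event row.

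**The case against.** The best defence is that the risk is low and the setting is watched. The exercise is 15 minutes of seated pedalling at self-rated intensity. Women are screened with a readiness questionnaire and cleared by a physician. Every session is supervised inside a radiotherapy department that they attend on treatment days. Safety is not among the three aims or the listed outcomes. All of this stands, and it limits the importance of the point. It does not supply a record, because no duty to ask about or write down an event is attached to the supervision.

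A second defence is that the sentence on log content describes adherence data and need not list every field. That also stands: Appendix H is not in the text available, so the absence of a symptom field is an inference from that sentence. A field on that form would still leave controls, who keep no exercise log, without an equivalent.

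Three stronger readings are tempting and are not supported:

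- A reader might infer that nobody could act on a symptom before week 4. Table 1 fixes when a study assessment is made; it does not say that supervising or treating staff ignore symptoms until then.
- A reader might infer that event recording is biased against the exercise arm. T1 and T2 are the same in both arms. A difference would arise only if events noticed at supervised sessions were recorded and counted, which the document neither requires nor rules out.
- A reader might multiply 20 sessions by 40 women and treat the resulting 800 as a measure of harm. It is a count of exposure at full attendance. The document gives no event or withdrawal rate from which missed events could be estimated.

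**Conclusion.** The point holds as a gap in the schedule that is inexpensive to close. What is firm: adverse events are scheduled only at T1 and T2; up to 20 sessions (300 minutes) per woman come before the first question at full attendance; and a woman who withdraws before T1 has no scheduled adverse event record. What is likely but depends on an unseen form: the log does not capture why a session was shortened or missed, which limits the adherence result for Aim 2. What depends on assumed course length and on the anchor for T2: late recall of events after T1 on long courses, and a delay of about a week or less on courses of 15 to 20 fractions. The number of events that would be missed cannot be estimated. The fatigue analysis is unaffected; what suffers is any statement about tolerability and the reading of adherence.

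**What to change.** - In Table 1, add an adverse event assessment at early withdrawal, for both arms.
- Add one brief adverse event question, worded identically for both arms and asked at existing radiotherapy attendances, for example weekly.
- Add to the exercise log (Appendix H) a reason for each shortened or missed session, with symptom as one option alongside clinic closure, machine failure and unavailability. If the form already has such a field, say so in Study retention and adherence.
- In Statistical analysis, state that any comparison of events between arms uses only the questions asked identically in both arms. Report events found through the log separately, for the exercise arm only.
- Reconcile Study Design, Assessments and Statistical analysis on when T1 falls, and state from which point the follow-up visit is counted.

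Cost: a revised log, a few ticks in Table 1 and a little data entry. A weekly question adds at most three askings per woman before T1 (weeks 1 to 3), or 3 × 80 = 240 across the trial, plus one to three per woman on courses assumed to run 25 to 33 fractions. The recorded event count will be somewhat higher. No new visit, procedure or staff is needed, since women already attend for treatment and a research assistant already collects the logs.

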TITLE: A Randomized Controlled Trial of Exercise to Reduce Cancer Related Fatigue in Women Undergoing Radiation Treatment for Breast Cancer

PROTOCOL #: Pro2016-XXXX

STUDY DRUG: N/A

IND #: N/A

SPONSOR: Hackensack University Medical Center

PRINCIPAL INVESTIGATOR: [name].
Lombardi Comprehensive Cancer Center
[name]., Ph.D.
Hackensack University Medical Center

ORIGINAL

PROTOCOL VERSION: Version 1.0 – 15 Feb 2016

A Randomized Controlled Trial of Exercise to Reduce Cancer Related Fatigue in Women Undergoing Radiation Treatment for Breast Cancer

[name]., Ph.D. (HUMC)
[name]. (HUMC)
[name]. (HUMC)
[name]. (HUMC)
[name]. (HUMC)

[name]. (LCCC)
[name]. (LCCC)
[name]., Ph.D. (LCCC)

b. ABSTRACT

Cancer related fatigue (CRF) is a common and debilitating side effect of radiotherapy in breast cancer patients. Physical activity interventions can attenuate CRF. The proposed study is a randomized, controlled trial (RCT) of exercise of structured moderate-intensity exercise intervention, delivered concurrently with radiotherapy, to reduce CRF and improve health-related quality of life among breast cancer patients. Eighty women with breast cancer scheduled to receive radiation therapy at HUMC will be randomized to one of the two trial arms: 1) a facility-based aerobic exercise utilizing a portable stationary pedal exerciser; or 2) a control group. Intervention arm participants will exercise at the hospital either before or after their radiation treatment. Assessments will be conducted at baseline, 4 weeks into radiation course, and at 4-week follow-up visit. The outcome variables are CRF, biomarkers of inflammation, and health-related quality of life. The study will provide preliminary evidence on whether a short-term moderate-intensity exercise intervention might be effective in reducing CRF in women undergoing radiotherapy for breast cancer, and whether this effect is mediated by inflammation.

c. Specific Aims

The specific aims of this study are: (1) to test the efficacy of a structured, moderate intensity exercise intervention delivered concurrently with radiation therapy (RT) in reducing CRF among breast cancer patients; (2) to provide pilot data on the acceptability and adherence of the exercise intervention on women receiving treatment; and (3) to determine the impact of exercise on serum inflammation markers among women undergoing RT.

d. Background

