CRF will be determined using the Functional Assessment of Chronic Illness Therapy (FACIT-Fatigue) survey instrument. The FACIT is a 13-item subscale developed to identify a finite set of concerns specific to fatigue. The responses to the 13 items on the FACIT-Fatigue questionnaire are each measured on a 4-point likert scale, with score ranging from 0 to 52. The FACIT-Fatigue scale has been validated in patients with cancer and showed excellent internal consistency and reliability. The following biomarkers of inflammation will be assessed at the Hackensack UMC: (1) High sensitivity CRP (hsCRP) - Serum hsCRP will be measured on the Vitros 5,1 FS Chemistry platform via an immunoassay with a reportable range of 0.10 -15.00 mg/L, and intra- and inter-assay CVs of 1.8-4.0%. (2) Serum fibrinogen and (3) Ferritin will be measured using standardized clinical protocols. All assays have intra- and inter-assays coefficient of variations <10%. We will collect CBC data at each blood draw for correlative and explorative purposes.

Secondary Outcomes

Cancer-related healthcare quality of life (HRQOL) among participants in the study will be measured using the Functional Assessment of Cancer Therapy (FACT) system questionnaires. The HRQOL measures four different domains (physical well-being, functional well-being, emotional well-being, and social/family well-being). FACT-B is a breast cancer specific module that will be used to reflect patients' concerns; moreover, they are reliable, reproducible, and have been validated in numerous studies. Higher scores on the FACT questionnaires reflect higher QOL. Post hoc analysis will be performed to associate RT treatment parameters against differences in outcomes, including utilizing the following pre-specified parameters: heart V5, lung V20, utilization of suprACLAVICULAR field (yes/no), utilization of suprACLAVICULAR field with axillary coverage (yes/no). These will potentially be hypothesis-generating and no Bonferroni corrections will be applied.

Sample size Considerations

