In this study participants are randomized into two groups: a structured exercise intervention group and a usual care control group. It is expected that there will be two levels of fatigue measurements: at baseline and after the exercise intervention. Our sample size calculation is based on analysis of covariance (ANCOVA) comparing mean fatigue score differences between the two intervention arms at the end of intervention, adjusting for baseline. In our exercise intervention study ([name] et al, unpublished data, mean fatigue scores of 42.53 (SD=9.35) and 37.12 (SD=9.42) were reported for the intervention and control arms, respectively. In the same study, the correlation coefficient between baseline and after intervention fatigue scores was calculated as 0.64. With the above guidelines and a level of significance of $\alpha=0.05$ (two-sided), we will use randomize 40 women/arm to obtain statistical significance between the arms with 90% power for the overall ANCOVA F-ratio.

Statistical analysis

Baseline characteristics will be compared between the two intervention groups using two-sample t-test or Wilcoxon rank-sum test depending on whether the t-test assumptions are satisfied or not. Suitably transformed variables will be used when necessary. Categorical variables will be compared between the two groups using chi-square tests or Fisher's exact test. The major analytical tool for addressing the specific aims of this study is linear mixed modeling for repeated measures. Study endpoints will be measured three times in each participant in the study, and it is expected that measures on the same individual will be correlated. We will also examine whether the variance of repeated measures changes over time. An appropriate correlation structure will be selected depending on whether there is a trend of variance with time or not. For each outcome measure of interest, a linear mixed repeated measures model will be fit to evaluate the main effects of time, study group, and group-by-time interaction. Known confounders and other covariates will be included in the linear mixed models if their individual bivariate associations with both the group variable and outcome are significant at 10% level.

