We hypothesize that participants in the intervention group will have lower average fatigue scores compared to the usual care group after the intervention. For Aim 1 and Aim 3, "change scores" will be defined as the difference between baseline score and 4 week, (end of radiation treatment) score. Change scores will be compared between the two groups using t-test or Wilcoxon rank-sum test. An ANCOVA model will be utilized to assess group differences in change scores adjusting for covariates including age. We hypothesize that participants in the structured exercise intervention group will have lower levels of fatigue (Aim 1) and lower levels of inflammatory biomarkers (Aim 3) compared to baseline at follow-up visits as compared to the usual care control group. We hypothesize that there will be at least partial normalization of both the fatigue levels reported and the inflammatory biomarkers to baseline by the 4-week follow-up visit. Linear mixed models as described above will be used to compare fatigue scores and inflammatory biomarkers levels over time across the study groups. For Aim 2, we will report rates of acceptability and adherence at baseline and end of intervention. We will use the binomial test to compare acceptance and adherence rates between the two intervention arms. Baseline and end of intervention acceptability levels evaluated using the Wilcoxon sign-rank test or McNemar's test (or generalized McNemar's test) for numerical and categorized outcomes, respectively.

A Graduate Research Assistant (GRA) will assist with data collection for the survey data. The GRA will collect log data of the women exercising using the Pedlar device. There is an hourly reimbursement for GRA labor without incentive. This has been approved via the Development Grant.

f. Significance

This study will contribute to the literature on the role of concurrent radiation treatment and moderate-intensity exercise in reducing cancer-related fatigue and improving HRQOL among breast cancer patients undergoing.

This study will also provide pilot data on the correlation of inflammatory markers with exercise-related changes in fatigue and other HRQOL measures in breast cancer patients undergoing RT. The strengths of this study include the use of an “in-office” easy to use exercise intervention that reduces participant burden, the timing of exercise inception that coincides with RT inception, and use of biomarkers.

g. Future Plans

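### Fatigue and three blood markers are listed together as primary outcomes with no order, error control or single deciding fatigue test, though the trial is sized on fatigue alone

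*Combined protocol and SAP*

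**What the plan says.** All references are to the combined protocol and SAP.

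- **Outcomes (section e).** The heading "Primary outcomes" is plural. Beneath it comes FACIT-Fatigue and then the markers: "The following biomarkers of inflammation will be assessed at the Hackensack UMC: (1) High sensitivity CRP (hsCRP", followed by fibrinogen and ferritin. Only quality of life stands under the secondary heading. Blood counts are set apart as exploratory; the three markers carry no such label.
- **Specific Aims (section c).** Aim 1 is "to test the efficacy of a structured, moderate intensity exercise intervention" against fatigue. Aim 3 asks what exercise does to serum inflammation markers.
- **Sample size Considerations.** The calculation is for an ANCOVA "comparing mean fatigue score differences between the two intervention arms at the end of intervention, adjusting for baseline", at two-sided 0.05 with 90% power and 40 women per arm. It contains no marker.
- **Statistical analysis.** The section first says "The major analytical tool for addressing the specific aims of this study is linear mixed modeling for repeated measures". It then defines one change score, baseline to 4 weeks, for Aims 1 and 3 alike, and continues: "Change scores will be compared between the two groups using t-test or Wilcoxon rank-sum test". Next: "An ANCOVA model will be utilized to assess group differences in change scores adjusting for covariates including age". The hypothesis is joint: "lower levels of fatigue (Aim 1) and lower levels of inflammatory biomarkers (Aim 3) compared to baseline at follow-up visits", relative to control. No testing order, gatekeeping or split of alpha is given.
- **Multiplicity.** The only sentence on the subject declines Bonferroni correction, and it belongs to the post hoc analyses of radiation parameters.
- **Future Plans (section g).** The marker data are described as pilot data from which endpoints for later work will be proposed.

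**The concern.** There are two linked gaps.

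First, the outcome list does not match the rest of the design. The title, the efficacy wording of Aim 1 and the whole sample size point to fatigue as the lead outcome, but the list puts three markers beside it on equal terms. Someone checking a trial report against this protocol would find that a difference in ferritin alone, with none in fatigue, matches a listed primary outcome.

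Second, calling fatigue primary would not settle the matter, because four analyses could each claim to decide it: the ANCOVA used for sizing, a t-test or Wilcoxon test on change, an ANCOVA on change, and a mixed model. They do not have the same power, and a choice made after seeing the data would not hold the error rate at 5%.

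The study is preliminary and ties no go/no-go decision to a p-value. What is at stake is a mislabelled claim, and endpoints for later work chosen partly on the strength of it.

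**Working it through.** **Inputs from Sample size Considerations.** Means 42.53 (SD 9.35) and 37.12 (SD 9.42); baseline to follow-up correlation 0.64; two-sided alpha 0.05; 40 per arm; stated power 90%.

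**1. The plan's own figure.**
- Difference: 42.53 − 37.12 = 5.41.
- Pooled SD: √((9.35² + 9.42²)/2) = 9.385.
- ANCOVA residual SD: 9.385 × √(1 − 0.64²) = 7.211.
- Noncentrality: 5.41 / (7.211 × √(2/40)) = 3.355, with 80 − 3 = 77 df. Power = 91.2%.
- For 90% power, 38 per arm are needed by the normal approximation and 39 by the noncentral F.

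The stated 40 per arm is reproduced for fatigue as the only primary outcome at the full 0.05.

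**2. The same design analysed by a change-score t-test.** This assumes that baseline and follow-up SDs are equal, which the plan does not state.
- SD of change: 9.385 × √(2 × (1 − 0.64)) = 7.963.
- Noncentrality: 5.41 / (7.963 × √(2/40)) = 3.038, with 78 df. Power = 85.1%.
- For 90% power, 46 per arm would be needed (normal approximation).

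**3. Error across the listed outcomes.** Assumptions: no true effects, one test per outcome at two-sided 0.05, and any one significant result counts.
- Independent: four outcomes, 1 − 0.95⁴ = 18.5%; three markers, 1 − 0.95³ = 14.3%.
- Equal pairwise correlation r (assumed, since the plan gives none), k tests, c = 1.96: error = 1 − ∫ [Φ((c − √r·u)/√(1 − r)) − Φ((−c − √r·u)/√(1 − r))]ᵏ φ(u) du.

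| r | four outcomes | three markers |
|---|---|---|
| 0 | 18.5% | 14.3% |
| 0.3 | 17.4% | 13.6% |
| 0.5 | 15.6% | 12.5% |
| 0.7 | 13.0% | 10.9% |
| 0.8 | 11.4% | 9.8% |

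**4. Error within fatigue, for one pair of tests.** If either the change-score t-test or the baseline-adjusted ANCOVA could decide, the two statistics correlate at √((1 + 0.64)/2) = 0.906. The bivariate normal then gives a 7.0% chance that at least one is significant under the null (6.9% by simulation at 40 per arm, 200,000 trials).

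**5. Two alternatives to a single primary outcome.**
- Keep all four as primary with Bonferroni, 0.05/4 = 0.0125: fatigue power at 40 per arm falls to 78.5%, and 90% power needs 51 (normal) to 53 (noncentral F) per arm.
- Test fatigue at 0.05 and, separately, the markers by Holm at 0.05 with no gate: 1 − 0.95² = 9.75% overall if independent.

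**The case against.** The strongest reply is that the harm rests on silence. The plan nowhere says that any one outcome, or any one marker, is enough for success. Aims 1 and 3 are separate questions, and statisticians differ on whether separate aims need joint error control. This stands. A reader might take 18.5% to be the trial's error rate; the documents do not support that, because the figure depends on a rule they never state. The 14.3% for Aim 3 alone needs the same kind of assumption.

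A reader might also infer that the plan calls the marker data pilot data throughout and so contradicts its own list at every turn. It does not. The phrase in Significance (section f) concerns the correlation of markers with changes in fatigue and quality of life, not the comparison between arms; only Future Plans applies it to the markers generally. The abstract calls the evidence on fatigue preliminary too, and Aim 3 could be read as support for listing the markers deliberately. The firmer evidence for fatigue as lead is the title and the sample size.

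Nor does the text show that the ANCOVA on change omits baseline. Age is given as one covariate among others, and with baseline included that model gives the same group test as the sizing ANCOVA. The 7.0% describes one pair of tests and leaves out the mixed model, so it is not the plan's error rate.

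Finally, preferring ANCOVA to the mixed model is partly taste. A baseline-adjusted mixed model can supply one named 4-week contrast and uses partial follow-up.

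None of this removes the mismatch between the outcome list and the sizing, or the absence of a deciding test for fatigue.

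**Conclusion.** The concern holds as a contradiction in labelling together with an unnamed deciding test. It should be corrected before analysis, but it does not invalidate the trial, and the sample size arithmetic is sound.

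That four measures are listed as primary, tested alike and without order, while one is sized, is read directly from the text. The error rates of 11.4% to 18.5% are illustrative: they rest on an assumed any-one-counts rule, one test per outcome and assumed correlations. The power gap between two candidate fatigue tests, 91.2% against 85.1%, uses the plan's own inputs, complete data and, for the change score, equal SDs. Power for the markers cannot be computed, because the plan gives no effect or SD for them.

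**What to change.** 1. Name FACIT-Fatigue at T1 as the single primary outcome, tested at two-sided 0.05. T1 is the 4-week assessment, which the Statistical analysis section equates with the end of radiation. Table 1 says only 4 weeks, and fractionation is left to the treating oncologist, so the plan should state that the T1 assessment is meant.
2. Name one baseline-adjusted test in advance: the ANCOVA on which the trial is sized or, answering the same question, the T1 contrast from a baseline-adjusted mixed model. Label the other fatigue analyses supportive and the T2 comparisons secondary.
3. Move hsCRP, fibrinogen and ferritin to secondary or exploratory, with no confirmatory claim. If a marker claim is wanted, test the markers only if fatigue is significant, with Holm across the three, so that overall error stays at 5%.

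**Cost.** Wording in the outcome and analysis sections, with no new data and no change in the 40 per arm. By the sizing ANCOVA, fatigue power is 91.2% with complete data; the plan gives no dropout rate, and at an assumed 10% loss (36 per arm) it is 88.1%. The downside is that a lone marker result can no longer be called a primary finding. If ANCOVA is chosen, the mixed model also becomes supportive for fatigue.
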